- Process of care/adherence variables:

Time from:

- Hospital admission to ICU/HDU admission
- Hospital admission to first diagnosis of suspected sepsis or suspected septic shock
- Randomisation to first research blood sample taken
- First blood sample taken to first blood sample delivered to laboratory

Analysis

Outcome definitions

The primary outcomes of the trial are (i) total duration of antibiotic treatment to 28 days following randomisation (superiority) measured in days as primary clinical effectiveness outcome, and (ii) 28-day all-cause mortality (non-inferiority) following randomisation as primary safety outcome. For the clinical effectiveness outcome, the use of antibiotics data will be recorded to the point where the participant stopped antibiotics. The use of antibiotics will also be recorded if participants either restarts antibiotics in hospital or discharged from hospital and the re-admitted and receives systemic antibiotics or discharged with antibiotics provided that these events are within 28 days following randomisation. The duration of antibiotics use will be calculated for each participant as the sum of the duration of each course of antibiotics administered from randomisation to day 28. For the safety outcome, all-cause mortality status on day 28 following randomisation will be recorded.

The Secondary effectiveness and safety outcome measures to 28 days following randomisation are

- Antibiotic duration and dose for the initial sepsis episode (duration in days from randomisation and dose measured as Defined Daily Dose)
- Antibiotic dose (measured as Defined Daily Dose)
- Unscheduled care escalation/re-admission
- Infection relapse/recurrence requiring further antibiotic treatment
- Super-infection defined as new infection at a different anatomical site
- Suspected antibiotic adverse reactions
- Time to 'fit' for hospital discharge

The 90-days all-cause mortality will also be analysed as secondary outcome using linked data, for example, from NHS Digital and the Intensive Care National Audit and Research Centre.

Analysis methods

Participants' baseline characteristics and outcomes will be summarised mean and standard deviation if data are continuous or frequency and percentage if data are categorical. The median and interquartile range will be presented if data are non-normal.

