Secondary outcomes will be assessed using an ITT approach. Continuous secondary outcomes will be analysed in the same way to the primary outcome and the categorical outcomes will be assessed using mixed effects logistic regression models. Time-to-event outcomes will be analysed using Cox

proportional hazards models. For all analyses, the adjusted effect estimates will be presented along with their associated 95% confidence interval (CI). In addition, the primary outcomes will also be analysed using Bayesian method as secondary analysis considering both non-informative and informative priors.

Exploratory sub-group analyses for primary effectiveness outcome will be reported using 99% confidence intervals. Linear mixed effect regression will be used with interaction terms (treatment group by sub-group) to estimate sub-group effects. The following sub-groups selected from a recent report about the management of infection causing sepsis in the NHS will be explored:

- Community-acquired pneumonia (CAP)
- Hospital-acquired pneumonia (HAP)
- Urinary tract infection (UTI)
- Intra-abdominal infection
- Infection with positive blood culture

In addition, community acquired, hospital acquired infections and SARS-COV-2 will be analysed as subgroup. Moreover, we will do the following subgroups analysis

- Sepsis vs Septic Shock
- Ward vs ICU where the intervention was stopped
- Surgery vs non-surgery on previous 72 hours

An exploratory analysis will be done to investigate weekend effect on the primary effectiveness outcome, the total duration of antibiotic treatment to 28 days from randomisation. Monitoring of the protocol processes and compliance measures is important in this trial (as detailed in section 4). These measures will be monitored and reported to the DMC throughout the trial. A final summary of the protocol processes and compliance will be presented at the end of the trial.

Handling missing data

Every effort will be made to minimise missing data both in baseline and outcome in the trial. Missing data will be assessed carefully. For the primary outcome (duration of antibiotics), start and stop dates for each course of antibiotics are required in order to compute the total duration for each participant. There will be no missing for start dates as the start dates and times will be the

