The frequency and percentages of serious adverse event and adverse event in the trial will be compared between the treatment arms using either chi-square test or Fisher's exact test for which the p-values will be reported. The event type, severity assessment, expectedness and relatedness to intervention will also be summarised by treatment arm.

Statistical software

The statistical analyses will be conducted in Stata SE version 17.0.

Health economic analysis plan

Decision-analysis modelling will be used to estimate for cohorts receiving each treatment protocol and standard care, the expected costs incurred and patient outcomes; patient outcomes will be evaluated in terms of quality-adjusted life years (QALYs). From these results, incremental cost per QALY ratios will be estimated for the two treatment protocols and standard care. These cost per QALY ratios will be used to form an efficiency frontier which will indicate the most cost-effective strategy at chosen cost per QALY thresholds. Results will be presented at two time periods: firstly, at the end of the study, as directed by the funder's brief, and secondly using a mathematical model employing a time horizon of a patient's lifetime, in order that the long-term consequences of avoided mortality or morbidity are appropriately captured.

The structure and methodology used within the mathematical model will be determined when the data are available in order to select the most appropriate approach. The model will be populated with trial data and will include key outcomes such as: rates of mortality; costs associated with length of stay for the index hospitalisation, including escalation of care; costs associated with readmission; and costs associated with antibiotic use. Extrapolations will be made based on the outcomes for each arm at the end of the study resulting in estimates of absolute costs and QALYs for each cohort conditional on the proportion of patients who are alive, and of these, the proportion that would have reduced health-related quality of life in the future. The modelling undertaken will be fully compliant with the current recommendations provided by the National Institute for Health and Care Excellence related to the methods of technology appraisal and will include any changes to this guidance before completion of the work. Extensive sensitivity analyses will be conducted in order to assess the robustness of the results to changes in key assumptions and parameter values.

References

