Table 21: Summary of total duration of antibiotic treatment from randomisation to 28 days by treatment group (Primary outcome)

	Standard care	PCT	CRP	PCT vs. Standard care Adjusted mean difference (95% CI)	CRP vs. Standard care Adjusted mean difference (95% CI)
Duration of antibiotic treatment to 28 days (days)					
N	xx.xx	xx.xx	xx.xx		
Mean (SD)	xx.xx	xx.xx	xx.xx		
Median (IQR)	xx.xx	xx.xx	xx.xx		
Missing	xx.xx	xx.xx	xx.xx		

Primary safety outcome

Table 22: Summary of 28-day all-cause mortality by treatment group (Primary outcome)

	Standard care	PCT	CRP	PCT vs. Standard care Adjusted OR (95% CI)	CRP vs. Standard care Adjusted OR (95% CI)
Mortality status 28 days post randomisation					
Dead	n (%)	n (%)	n (%)		
Alive	n (%)	n (%)	n (%)		
Missing	n (%)	n (%)	n (%)		

Secondary effectiveness and safety outcomes to 28 days

Table 23: Summary of secondary effectiveness and safety outcomes by treatment group

	Standard care	PCT	CRP	PCT vs. Standard care Adjusted estimate (95% CI)	CRP vs. Standard care Adjusted estimate (95% CI)
Mortality status 90 days post randomisation					
Dead	n (%)	n (%)	n (%)		
Alive	n (%)	n (%)	n (%)		
Missing	n (%)	n (%)	n (%)		
Antibiotic dose (Daily Defined Dose)					
N	xx.xx	xx.xx	xx.xx		
Mean (SD)	xx.xx	xx.xx	xx.xx		
Median (IQR)	xx.xx	xx.xx	xx.xx		
Missing	xx.xx	xx.xx	xx.xx		
Patient required unscheduled care escalation					
No	n (%)	n (%)	n (%)		
Yes	n (%)	n (%)	n (%)		
Missing	n (%)	n (%)	n (%)		
Number of unscheduled care escalations					
1	n (%)	n (%)	n (%)		

	2	n (%)	n (%)	n (%)		
	...	n (%)	n (%)	n (%)		
	Total	n	n	n		
	Missing	n (%)	n (%)	n (%)		
Patient had infection relapse/recurrence requiring further antibiotic treatment						
	No	n (%)	n (%)	n (%)		
	Yes	n (%)	n (%)	n (%)		
	Missing	n (%)	n (%)	n (%)		
Number of infection relapses/recurrences						
	1	n (%)	n (%)	n (%)		
	2	n (%)	n (%)	n (%)		
	...	n (%)	n (%)	n (%)		
	Total	n	n	n		
	Missing	n (%)	n (%)	n (%)		
Number of super-infections defined as new infection at a different anatomical site						
	1	n (%)	n (%)	n (%)		
	2	n (%)	n (%)	n (%)		
	...	n (%)	n (%)	n (%)		
	Total	n	n	n		
	Missing	n (%)	n (%)	n (%)		
Time from randomisation to first 'fit' for hospital discharge						
	N	xx.xx	xx.xx	xx.xx		
	Mean (SD)	xx.xx	xx.xx	xx.xx		
	Median (IQR)	xx.xx	xx.xx	xx.xx		
	Missing	xx.xx	xx.xx	xx.xx		

Subgroup analyses

Table 24: Sub-group analyses on the duration of antibiotic days from randomisation to day 28

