Surgical ward	n (%)	n (%)	n (%)	
Another critical care unit	n (%)	n (%)	n (%)	
Other	n (%)	n (%)	n (%)	
Missing	n (%)	n (%)	n (%)	
Core body temperature (°C)				
N	n (%)	n (%)	n (%)	x.xx
Mean (SD)	n (%)	n (%)	n (%)	
Median (IQR)	n (%)	n (%)	n (%)	
Missing	n (%)	n (%)	n (%)	
White cell count (x10⁹/L)				
N	xx.xx	xx.xx	xx.xx	x.xx
Mean (SD)	xx.xx	xx.xx	xx.xx	
Median (IQR)	xx.xx	xx.xx	xx.xx	
Missing	xx.xx	xx.xx	xx.xx	
Infection acquirement				
Community acquired	n (%)	n (%)	n (%)	x.xx
Hospital acquired	n (%)	n (%)	n (%)	
Missing	n (%)	n (%)	n (%)	
Site of infection causing sepsis*				
Respiratory tract	n (%)	n (%)	n (%)	x.xx

If yes above, was it pneumonia	n (%)	n (%)	n (%)	x.xx
If yes above (pneumonia), was it ventilator related	n (%)	n (%)	n (%)	x.xx
Central nervous system	n (%)	n (%)	n (%)	x.xx
Skin and soft tissue	n (%)	n (%)	n (%)	x.xx
Is yes above, was it a surgical site infection	n (%)	n (%)	n (%)	x.xx
Central line related infection	n (%)	n (%)	n (%)	x.xx
Intra-abdominal	n (%)	n (%)	n (%)	x.xx
Urinary tract	n (%)	n (%)	n (%)	x.xx
If yes above, was it associated with a urinary catheter	n (%)	n (%)	n (%)	x.xx
Ear, nose and throat	n (%)	n (%)	n (%)	x.xx
Blood stream	n (%)	n (%)	n (%)	x.xx
If yes above, was it primary	n (%)	n (%)	n (%)	x.xx
Unknown focus	n (%)	n (%)	n (%)	x.xx
Other	n (%)	n (%)	n (%)	x.xx
Is there a causative microorganism identified for the infection causing sepsis				
No	n (%)	n (%)	n (%)	x.xx
Yes	n (%)	n (%)	n (%)	
Missing	n (%)	n (%)	n (%)	
Pathogens				
	n (%)	n (%)	n (%)	x.xx
	n (%)	n (%)	n (%)	

* Each site of infection is summarised separately for all participants. Therefore, it is possible that participants report more than one presumed site of infection causing sepsis.

Table 29: Baseline outcome measures comparing pre-COVID participants versus participants recruited during COVID

Outcome	Pre-COVID	During Covid	Total	P-Value	
qSOFA	N			x.xx	
	Mean (SD)	xx.xx	xx.xx		xx.xx
	Median (IQR)	xx.xx	xx.xx		xx.xx
	Missing	xx.xx	xx.xx		xx.xx

SOFA				x.xx	
	N	xx.xx	xx.xx		xx.xx
	Mean (SD)	xx.xx	xx.xx		xx.xx
	Median (IQR)	xx.xx	xx.xx		xx.xx
	Missing	xx.xx	xx.xx	xx.xx	
APACHE II				x.xx	
	N	xx.xx	xx.xx		xx.xx
	Mean (SD)	xx.xx	xx.xx		xx.xx
	Median (IQR)	xx.xx	xx.xx		xx.xx
	Missing	xx.xx	xx.xx	xx.xx	

SECTION 6 - ADVERSE EVENTS AND SERIOUS ADVERSE EVENTS

Table 30: Summary of suspected clinically relevant antibiotic related events during inpatient stay (includes events during readmissions)

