	Standard care	PCT	CRP	Total	PCT vs. Standard care Adjusted estimate (95% CI)	CRP vs. Standard care Adjusted estimate (95% CI)
Number of days patients experienced a suspected clinically relevant antibiotic related event						
N	xx.xx	xx.xx	xx.xx	xx.xx		
Mean (SD)	xx.xx	xx.xx	xx.xx	xx.xx		
Median (IQR)	xx.xx	xx.xx	xx.xx	xx.xx		
Missing	xx.xx	xx.xx	xx.xx	xx.xx		
Number of patients experiencing each of the following events						
Anaphylaxis	n (%)	n (%)	n (%)	n (%)		
Gastrointestinal	n (%)	n (%)	n (%)	n (%)		
Haematological	n (%)	n (%)	n (%)	n (%)		
Hepatobiliary	n (%)	n (%)	n (%)	n (%)		
Renal	n (%)	n (%)	n (%)	n (%)		
Neurological	n (%)	n (%)	n (%)	n (%)		
Dermatological	n (%)	n (%)	n (%)	n (%)		
Cardiac	n (%)	n (%)	n (%)	n (%)		
Muscular	n (%)	n (%)	n (%)	n (%)		
Other	n (%)	n (%)	n (%)	n (%)		
Missing	n (%)	n (%)	n (%)	n (%)		
Patient experienced proven new Clostridium difficile diarrhoeal infection						
N	xx.xx	xx.xx	xx.xx	xx.xx		
Mean (SD)	xx.xx	xx.xx	xx.xx	xx.xx		
Median (IQR)	xx.xx	xx.xx	xx.xx	xx.xx		
Missing	xx.xx	xx.xx	xx.xx	xx.xx		
Patient experienced a proven new infection with a multi-drug resistant organism						
N	xx.xx	xx.xx	xx.xx	xx.xx		
Mean (SD)	xx.xx	xx.xx	xx.xx	xx.xx		

Median (IQR)	xx.xx	xx.xx	xx.xx	xx.xx	
Missing	xx.xx	xx.xx	xx.xx	xx.xx	

Table 31: Summary of suspected clinically relevant antibiotic related events post hospital discharge to 28 day follow-up

	Standard care	PCT	CRP	Total	PCT vs. Standard care Adjusted estimate (95% CI)	CRP vs. Standard care Adjusted estimate (95% CI)
Number of days patients experienced a suspected clinically relevant antibiotic related event						
N	xx.xx	xx.xx	xx.xx	xx.xx		
Mean (SD)	xx.xx	xx.xx	xx.xx	xx.xx		
Median (IQR)	xx.xx	xx.xx	xx.xx	xx.xx		
Missing	xx.xx	xx.xx	xx.xx	xx.xx		
Number of patients experiencing each of the following events						
Anaphylaxis	n (%)	n (%)	n (%)	n (%)		
Gastrointestinal	n (%)	n (%)	n (%)	n (%)		
Haematological	n (%)	n (%)	n (%)	n (%)		
Hepatobiliary	n (%)	n (%)	n (%)	n (%)		
Renal	n (%)	n (%)	n (%)	n (%)		
Neurological	n (%)	n (%)	n (%)	n (%)		
Dermatological	n (%)	n (%)	n (%)	n (%)		
Cardiac	n (%)	n (%)	n (%)	n (%)		
Muscular	n (%)	n (%)	n (%)	n (%)		
Other	n (%)	n (%)	n (%)	n (%)		
Missing	n (%)	n (%)	n (%)	n (%)		
Patient experienced proven new Clostridium difficile diarrhoeal infection						
No	n (%)	n (%)	n (%)	n (%)		
Yes	n (%)	n (%)	n (%)	n (%)		
Missing	n (%)	n (%)	n (%)	n (%)		
Patient experienced a proven new infection						

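### Suspected antibiotic reactions are an outcome to day 28, but the table shells estimate arm differences only in two parts split at hospital discharge

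*SAP*

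**What the plan says.** Under Outcome definitions, the SAP opens its list with "The Secondary effectiveness and safety outcome measures to 28 days following randomisation are" and includes "Suspected antibiotic adverse reactions" in it. The window is therefore randomisation to day 28.

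Under Analysis methods, secondary outcomes follow intention to treat, and "the categorical outcomes will be assessed using mixed effects logistic regression models". The Safety section adds that "The frequency and percentages of serious adverse event and adverse event in the trial will be compared between the treatment arms", by chi-square or Fisher's exact test. Neither text names the 28-day reaction outcome or says how to construct it.

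The shells are as follows.

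- "Table 23: Summary of secondary effectiveness and safety outcomes by treatment group" has rows for 90-day mortality, antibiotic dose, care escalation, relapse, super-infection and time to being fit for discharge. It has none for antibiotic reactions.
- "Table 30: Summary of suspected clinically relevant antibiotic related events during inpatient stay (includes events during readmissions" (closing bracket omitted) has columns for adjusted PCT and CRP estimates against standard care. Its title sets no day-28 limit.
- "Table 31: Summary of suspected clinically relevant antibiotic related events post hospital discharge to 28 day follow-up" has the same comparison columns.
- Both split tables count days with an event and, under "Number of patients experiencing each of the following events", patients per event type. Neither has a row for any reaction, and no table joins the two periods.
- Tables 32 and 33 cover serious adverse events only and have no comparison column.

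**The concern.** Fewer adverse effects for patients is one of the reasons the SAP's background gives for tailoring antibiotic duration, so readers will look for this result. The shells direct the analyst to estimate it over two windows whose common boundary is hospital discharge. That boundary comes after randomisation, and the SAP itself treats length of hospital stay and time to being fit for discharge as outcomes, so it allows that the arms may differ there. Events after discharge can also occur only in people discharged alive, and the SAP does not say who forms the denominator of Table 31.

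An arm with shorter stays has less inpatient time in which a reaction can be counted and more time after discharge. Table 30 would then favour that arm and Table 31 would count against it, with no difference in toxicity.

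Two details of the shells make the split harder to use. Table 31 does not say whether events during a readmission are excluded, although these also fall after the first discharge. And Table 30 summarises new *C. difficile* infection and new multi-drug resistant infection by mean (SD) and median, although the row labels describe yes/no items and Table 31 lays out the same items as No/Yes.

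**Working it through.** The SAP states no figure on this point, so there is nothing to reproduce. The check has two parts.

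**1. Definition against shells**

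| Element | Defined outcome | Table 30 | Table 31 |
|---|---|---|---|
| Start | Randomisation | Inpatient stay | Hospital discharge |
| End | Day 28 | No day limit in title | Day 28 |
| Readmission events | Inside the window | Included | Not stated |
| Any-reaction row per patient | Needed | None | None |
| Adjusted arm estimates | Implied by Analysis methods | Yes | Yes |

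Neither table matches the defined window, and no other shell does.

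**2. What the split does when the true 28-day risk is equal**

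Assumed inputs, none of them in the SAP: 28-day risk R, constant daily hazard, index stay of L days, no deaths.

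- Hazard: h = −ln(1 − R)/28
- Inpatient risk: 1 − exp(−h·L)
- Post-discharge risk: 1 − exp(−h·(28 − L))

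*Fixed stay, R = 10%, 14 days against 12 days.* h = −ln(0.9)/28 = 0.003763.

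- Inpatient: 1 − exp(−0.003763 × 14) = 5.13%, and 1 − exp(−0.003763 × 12) = 4.42%. Odds ratio (0.0442/0.9558)/(0.0513/0.9487) = 0.85.
- Post-discharge: 5.13% for 14 days at risk and 5.84% for 16 days. Odds ratio 1.15.
- Over 28 days: 1 − 0.9487 × 0.9487 = 10% and 1 − 0.9558 × 0.9416 = 10%. Odds ratio 1.00.

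Across R = 5%, 10% and 20%, and stays of 14 v 13, 14 v 12, 14 v 11, 20 v 16 and 10 v 8 days, the inpatient odds ratio runs from about 0.78 to 0.93 and the post-discharge one from about 1.07 to 1.52. The 28-day odds ratio is 1.00 throughout.

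*Variable stay, R = 20%.* h = −ln(0.8)/28 = 0.00797. Stay is lognormal with coefficient of variation 1 and mean m of 12, 15 or 18 days. It is multiplied by (m − 2)/m in one arm, and the two risks are averaged over the distribution. The result depends on whether stay is capped at 28 days before or after the multiplication.

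| Mean stay | Inpatient risk, unchanged arm | Shorter arm, capped before | Fall (points) | Shorter arm, capped after | Fall (points) |
|---|---|---|---|---|---|
| 12 | 8.10% | 6.82% | 1.28 | 7.01% | 1.09 |
| 15 | 9.55% | 8.36% | 1.19 | 8.61% | 0.94 |
| 18 | 10.80% | 9.68% | 1.12 | 9.99% | 0.81 |

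The post-discharge risk rises by 1.2 to 1.3 points (capped before) or 0.8 to 1.1 points (capped after). The 28-day risk stays at 20% in both arms.

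**The case against.** The best defence is that the written plan already covers the outcome. Outcome definitions fixes the window, and Analysis methods fixes intention to treat and a mixed logistic model, with adjusted estimates and 95% confidence intervals. The shells are headed as templates, version 0.2, and are plainly incomplete: antibiotic duration for the initial episode and duration to ICU discharge also lack tables. A missing row is weak evidence that an analysis was dropped. This stands to the extent that a reader might infer the 28-day comparison will never be made, and the SAP does not support that. What remains is that the SAP does not define the 28-day variable, and the only shells for these events steer the adjusted estimates to the split windows.

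A reader might also infer that readmission events are counted twice. The bracket in the title of Table 30 can fairly be read as assigning them to that table, leaving Table 31 for events outside hospital. The SAP does not say so, so this is an ambiguity and not a demonstrated overlap. Nor do the mismatched formats of the infection items prevent a 28-day result, which would be derived from participant data and not by adding printed tables.

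The size is open to challenge too. A constant hazard over 28 days ignores exposure, and the sample size section assumes a mean antibiotic duration of 7 days (SD 6). If the hazard applies only on antibiotic days, with duration assumed lognormal and its correlation with stay 0 or 0.5, the inpatient fall is about 0.3 to 0.9 points. Deaths, assumed at 15% by day 28 in the SAP, are left out. These points reduce the size but do not change the direction, and no shift arises if stay is the same in all arms.

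**Conclusion.** The point holds and is worth correcting before analysis. A secondary safety outcome defined to day 28 has no matching row, and its only adjusted estimates in the shells are conditioned on the timing of discharge. The direction of the distortion follows from the layout whenever stay differs between arms. Its size is illustrative: about 0.8 to 1.3 percentage points each way under a 20% risk, mean stay of 12 to 18 days, a 2-day cut and a constant hazard, and less if reactions occur only during antibiotic exposure. The SAP gives no reaction rates and predicts no change in stay, so the shift in this trial cannot be computed. The primary outcomes are not affected.

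*C. difficile* and multi-drug resistant infection are not in the SAP's list of secondary outcomes, so the point is no ground for making them new inferential outcomes.

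**What to change.** - Add one row to Table 23: the proportion of all randomised participants with at least one suspected antibiotic reaction from randomisation to day 28, in or out of hospital, each participant counted once. Analyse it by the mixed effects logistic model already given under Analysis methods, and name it as the inferential comparison for this outcome.
- Make Tables 30 and 31 descriptive by removing the adjusted estimates.
- State that readmission events are counted in one of the two tables only, and which one.
- Limit Table 30 to day 28.
- Use No/Yes for the two infection items in Table 30. They may be shown descriptively to day 28.

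The cost is one more derived variable, a few lines of SAP text and corrected shells. Both periods are already tabulated, so no new data collection is apparent.

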Confidence intervals and p-values

All statistical tests will be two-sided at the 5% significance level except for the non-inferiority safety test that will use a 1-sided significance level of 2.5%⁷. The estimate, 95% confidence interval (95% CI) and P value will be reported for each test undertaken.

Analysis populations

All analyses will be based on 'Intention-to-treat' (ITT) following ICH E9 guidelines. The participants will be analysed according to the treatment they were randomised to, irrespective of the treatment they actually received. All participants will be included in the analysis, regardless of whether they adhered to the protocol.

The Per Protocol (PP) population is usually defined as all participants who completing the study without major protocol deviations. We will identify the participants in this study who completed the study without major protocol deviations and then perform a PP analysis as secondary analysis.

Adherence and protocol deviations

The idea of site protocol adherence has been developed over a series of TMG discussions. Protocol processes have been developed through 4 key steps to help identify 'protocol adherence' and will be closely monitored during the trial. These include assessment of blood samples, production of advice, delivery of advice and the decisions taken for antibiotic treatment.

Trial population

Screening data

A detailed summary of the screening data will be presented as frequencies and percentages to describe the representativeness of the trial sample. This will include total number of hospitalised adult patients screened for eligibility, and number (percentage) of patients randomised to intervention arms.

Eligibility

The ADAPT-Sepsis trial protocol provides full details of the eligibility criteria (inclusion/exclusion criteria). The eligibility will be summarised using frequencies and percentages to describe how many patients were:

- Eligible and randomised
- Eligible and not randomised (summarising the main reasons for not randomised)
- Ineligible and not randomised (summarising the main reasons for exclusion)
-

Recruitment

A Patient Flow diagram will be used to illustrate the flow of participants throughout the trial. This will include:

- Number of patients screened for eligibility
- Number of eligible patients randomised to each intervention arm
- Number of withdrawals, died and lost to follow-up after randomisation

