The primary effectiveness analyses will assess whether any of the biomarker interventions are better than standard care. The primary analysis approach for the duration of antibiotics will be intention-to-treat (ITT). ITT analysis will consist of all randomised patients and will assess the effect of treatment assignment. For the ITT analysis, linear mixed effects regression models will be fitted to estimate the treatment effect having adjusted for age, gender and the stratification variables (sepsis severity, recruiting centre (random effect) and surgery within the last 72 hours). After fitting the model, we will investigate the validity of the assumption of normality. Alternative methods of analyses will be considered if the distribution of the primary effectiveness outcome is non-normal. In this trial, participants may die before antibiotic therapy is discontinued. In such cases the outcome is undefined and is referred to as 'truncated by death'. A crude comparison between the survivors on each treatment arm may give rise to biased outcome comparisons. Therefore, we will consider undertaking some sensitivity analyses to estimate treatment effect having account for the deaths. This will explore different approaches to analysis of ICU trials, that allow incorporation of multiple relevant outcomes, including death, into a single overall measure (e.g., the win ratio⁸, global ranking score⁹, and weighted composite outcome¹⁰).

The primary safety outcome (28-day all-cause mortality) is based on assessing non-inferiority and we specify the null hypothesis that the biomarker interventions are much worse compared with standard-of-care. The primary safety outcome will be analysed using mixed effect logistic regression models, using the same adjustments variables as the primary effectiveness analysis. We will derive risk difference from the fitted logistic regression model to compare the non-inferiority margin for the safety outcome. The unadjusted and adjusted estimates and the 95% confidence intervals will be compared with the non-inferiority margin to accept/reject the null hypothesis. Therefore, our primary effectiveness outcome (antibiotic duration) will not provide all the information as regards the treatment effect. Safety (28-day all-cause mortality) is paramount - only if an intervention arm is not worse than the control (standard care only) will it be acceptable.

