with a multi-drug resistant organism	No	n (%)	n (%)	n (%)	n (%)		
	Yes	n (%)	n (%)	n (%)	n (%)		
	Missing	n (%)	n (%)	n (%)	n (%)		

Table 32: Serious adverse events (SAE) summarised by treatment group

		Standard care	PCT	CRP	Total
SAE's					
	Number of SAE's reported	n (%)	n (%)	n (%)	n (%)
Reason Serious Adverse Event deemed serious					
	Death	n (%)	n (%)	n (%)	n (%)
	Life-threatening	n (%)	n (%)	n (%)	n (%)
	Hospitalisation or prolongation of existing hospitalisation	n (%)	n (%)	n (%)	n (%)
	Persistent or significant disability or incapacity	n (%)	n (%)	n (%)	n (%)
	Congenital anomaly/birth defect	n (%)	n (%)	n (%)	n (%)
	Other	n (%)	n (%)	n (%)	n (%)
SAE severity assessment					
	Mild	n (%)	n (%)	n (%)	n (%)
	Moderate	n (%)	n (%)	n (%)	n (%)
	Severe	n (%)	n (%)	n (%)	n (%)
	Fatal/life threatening	n (%)	n (%)	n (%)	n (%)

Table 33: Assessment of SAE's summarised by treatment group

Assessment of SAE's		Standard care	PCT	CRP	TOTAL
SAE related to trial intervention:					
	Definitely	n (%)	n (%)		n (%)
	Probably	n (%)	n (%)		n (%)
	Possibly	n (%)	n (%)		n (%)
	Unlikely	n (%)	n (%)		n (%)
	Unrelated	n (%)	n (%)		n (%)
Expectedness of SAE:					
	Expected	n (%)	n (%)		n (%)
	Unexpected	n (%)	n (%)		n (%)
Outcome of event:					
	Resolved – no sequelae	n (%)	n (%)		n (%)
	Resolved – with sequelae	n (%)	n (%)		n (%)

	Unresolved	n (%)	n (%)		n (%)
	Death	n (%)	n (%)		n (%)

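### The SAE comparison names only p-values and Table 32 has no room for a contrast with standard care, so neither applies the SAP's own rule of an estimate and 95% CI for each test

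*SAP*

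**What the plan says.** Table numbers here follow the captions in the body of the template tables; the SAP's list of tables numbers the SAE tables differently.

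- **Safety section.** SAEs and other adverse events are to be set side by side for the three arms as counts and percentages. The method given is "using either chi-square test or Fisher's exact test for which the p-values will be reported". The section names no effect measure, no interval and no pair of arms. Event type, severity, expectedness and relatedness are to be summarised by arm.
- **Template tables, Section 6.** "Table 32: Serious adverse events (SAE) summarised by treatment group" has columns for standard care, PCT, CRP and total. Its first row is "Number of SAE's reported". There is no contrast column and no column for the p-value that the Safety section promises. "Table 33: Assessment of SAE's summarised by treatment group" has none either.
- **Confidence intervals and p-values.** "The estimate, 95% confidence interval (95% CI) and P value will be reported for each test undertaken".
- **Other shells.** Table 22 (28-day mortality), Table 23 (secondary outcomes) and Tables 30 and 31 (antibiotic-related events) each have one column for PCT against standard care and one for CRP against standard care, both with a 95% CI. Tables 10 to 12 (cause of death, withdrawals, deaths by period) have three arms and a single p-value column.

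**The concern.** The trial asks of each biomarker protocol separately how it compares with standard care. For SAEs, the plan does not fix that comparison. The wording of the Safety section fits one three-arm test or several pairwise tests, and the shell does not settle which. The single p-value columns in Tables 10 to 12 suggest the three-arm reading.

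A three-arm test asks whether the three proportions are all equal, so it responds to a PCT-CRP difference as much as to a difference from standard care. A non-significant result would tend to be reported as similar SAE rates with no upper limit on the excess in either arm. A significant result would not say which protocol, if either, differs from standard care. Under a pairwise reading, the Safety text and shell would still supply no estimate or interval, and the pairs would still be unnamed.

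**Working it through.** **Inputs.** The sample size is 2760 allocated 1:1:1, so 2760/3 = 920 per arm; with the stated 5% withdrawal, 920 × 0.95 = 874. The SAP gives no SAE rate and no figure for this comparison, so there is nothing of its own to reproduce. I assume about 10% in standard care, with 5% as a second case and 2% to 20% for the power check. All counts below are participants with at least one SAE, in the order standard care/PCT/CRP.

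**Formulas.** Three-arm Pearson statistic with equal arms: X² = Σ(xᵢ − x̄)² / [n·p̄(1 − p̄)], on 2 df, for which p = exp(−X²/2). Pairwise tests are the same statistic on two arms, 1 df, without continuity correction. Intervals at 874 per arm are Newcombe; those at 920 per arm are Wald.

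**Example 1: 87/101/114 of 874 (10.0%, 11.6%, 13.0%).**
- x̄ = 302/3 = 100.67; p̄ = 302/2622 = 0.1152.
- Σ(xᵢ − x̄)² = 186.8 + 0.1 + 177.8 = 364.7; n·p̄(1 − p̄) = 89.07.
- X² = 4.09; p = exp(−2.047) = 0.13.
- CRP against standard care: (114 − 87)/874 = +3.1 points, 95% CI 0.1 to 6.1, p = 0.043.
- PCT against standard care: +1.6 points, p = 0.28.

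**Example 2: 87/70/105 of 874 (10.0%, 8.0%, 12.0%).**
- x̄ = 262/3 = 87.33; p̄ = 262/2622 = 0.0999.
- Σ(xᵢ − x̄)² = 0.1 + 300.4 + 312.1 = 612.7; n·p̄(1 − p̄) = 78.61.
- X² = 7.79; p = exp(−3.897) = 0.020.
- PCT against standard care: p = 0.155. CRP against standard care: p = 0.169. PCT against CRP: p = 0.005, which drives the three-arm result.

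**The same at 5% and 920 per arm.** Counts 46/68/57 give three-arm p = 0.104, with PCT against standard care +2.4 points (95% CI 0.2 to 4.6, p = 0.033). Counts 46/59/34 give three-arm p = 0.029, with p = 0.19 and 0.17 against standard care and 0.008 for PCT against CRP.

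**How often the two analyses disagree (simulated trials, 874 per arm).**
- True rates 10/11.5/13%: among trials in which a biomarker arm shows a nominally significant excess over standard care, the three-arm test is non-significant in about 27%. That is about 15% of all trials.
- True rates 10/8/12%: about 26% of significant three-arm results come with neither contrast against standard care significant. That is about 19% of all trials.
- True rates 10/10/13%: the three-arm test is significant in 53% of trials, and a significant excess against standard care appears in 51%.

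**Power (non-central chi-square, 920 per arm, standard-care rate 2% to 20%, difference d set to give 80% pairwise power).**
- One arm raised by d, the other equal to standard care: three-arm power 84% to 88%.
- One arm raised by d, the other by d/2: three-arm power 71%.
- One arm up by d/2, the other down by d/2: three-arm power 75% to 89%, while the two contrasts with standard care have 30% to 34% (raised arm) and 33% to 54% (lowered arm).

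So the three-arm test loses power when the other biomarker arm is intermediate, gains a little when that arm equals standard care, and becomes significant for another reason when the biomarker arms move apart.

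**The case against.** Several stronger readings are tempting, and the SAP does not support them.

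- **That the plan fixes a three-arm test.** It does not; the wording is ambiguous. Tables 10 to 12 belong to the follow-up section and only suggest that reading. Both numerical examples depend on it.
- **That the plan omits estimates and intervals altogether.** The general reporting rule requires both. What stands is that the Safety section and Table 32 do not apply that rule: no measure is named, no pair of arms is named, and the table has no column for the result.
- **That SAEs are the only safety comparison without contrasts.** Tables 10 and 12 also have just a p-value by arm, although 28- and 90-day mortality get contrasts in Tables 22 and 23.
- **That acceptability of an arm turns on this table.** The statement that "only if an intervention arm is not worse than the control (standard care only) will it be acceptable" is explicitly about 28-day mortality, which has its own risk difference, interval and margin. Relapse, escalation, super-infection and antibiotic-related events also have both contrasts.
- **That an excess would be hidden.** Table 32 prints a number and percentage for each arm, so a raised arm would be visible. What is missing is its uncertainty.

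Two cautions on the figures also stand. The p-value of 0.043 is one of two unadjusted comparisons and would not pass 0.025. The examples count participants, whereas the first row of Table 32 counts SAE reports. One participant can have several reports, so a chi-square test on report counts would not rest on independent units.

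**Conclusion.** The point holds in limited form. The Safety section leaves the SAE comparison undefined between three-arm and pairwise, and with Table 32 it fails to carry out the SAP's rule on estimates and intervals. Neighbouring safety tables already use the appropriate layout.

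If the test is three-arm, it can disagree with the contrasts against standard care in either direction; in the two unfavourable scenarios, about a quarter of the relevant results do so. When only one biomarker arm is raised, detection is not impaired. What is lost is which arm is raised and an upper bound on the excess. The sizes rest on assumed SAE rates, on 874 or 920 participants per arm, and on counting participants.

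This is a cheap improvement to a supporting safety table. The mortality safety conclusion does not depend on it.

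**What to change.** In the Safety section, state that SAEs are compared as two contrasts, PCT against standard care and CRP against standard care. Each should be a risk difference in participants with at least one SAE, with a 95% CI; the chi-square or Fisher p-value for that pair can be kept as descriptive. In Table 32, add a row for participants with at least one SAE and the two contrast columns already used in Tables 30 and 31. The count of SAE reports can stay as a summary without a test.

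The cost is a sentence or two of SAP text, one row and two columns, with no new data. The downside is two unadjusted comparisons in place of one, which should be labelled descriptive.
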